#### 5.15.2. AE Severity Assessments

The guidelines outlined in Table 1 will be used for severity assessments.

**Note:** The term “severe” is a measure of intensity and a severe AE is not necessarily serious.

Table 1 Adverse Event Severity – Description of Severity Grades

Severity Grade	Description
Mild	Symptoms barely perceptible by the patient, do not affect his/her performance or activity, do not normally require the administration of drugs for relief of the symptoms but they may, however, be administered depending on the patient’s needs.
Moderate	Symptoms sufficiently serious to cause patient discomfort, having impact on the performance of daily activities; the patient may be able to continue in the study, but it may be necessary to treat the symptoms.
Severe	Symptoms cause serious discomfort and they may be serious to a degree that the patient may not be able to continue in the study; treatment may be administered for the symptoms and/or the patient hospitalized.

### 5.15.3. Adverse Event Relatedness Assessments

All AEs will be assessed for their relatedness to the study device or the procedures. An AE is considered device-related if there is a reasonable possibility that the device caused or contributed to the event. Information that “reasonably suggests” a causal relationship includes any information such as professional, scientific or medical facts and observations or opinions that would reasonably suggest that a device has caused or may have caused or contributed to the event. If the chance that a device may have caused or contributed to an event is very remote or very unlikely, the event should be considered not related to the device.

AE causality will be assessed using the guidelines outlined in Table 2.

Table 2: Adverse Event Causality Categories

Relationship	Comment
Definitely	This category applies to those AEs which the investigator feels are incontrovertibly related to the study treatment , study ulcer or study procedures. An AE may be assigned an attribution of definite if or when (must have all three): 
 
a) It follows a reasonable temporal sequence from application of the device.
 
b) It could not be reasonably explained by the known characteristics of the subject’s clinical state, environmental or toxic factors or other modes of therapy administered to the subject.
 
c) It follows a known response pattern to treatment with the device.
 

Probable	
This category applies to those AEs which, after careful medical consideration at the time they are evaluated, are felt with a high degree of certainty to be related to the device. An AE may be considered probable if or when (must have three):
 
 
a) It follows a reasonable temporal sequence from application of the device.
 
b) It could not readily have been produced by the subject’s clinical state, environmental or toxic factors, or other therapies administered to the subject.
 
c) Disappears or is decreased upon removal of the device.
 
d) It follows a known response pattern to treatment with the device.
 

Possibly	
This category applies to those AEs which, after careful medical consideration at the time they are evaluated, are judged unlikely but cannot be ruled out with certainty to the device. An AE may be considered possible if or when (must have two):
 
 
a) It follows a reasonable temporal sequence from application of the device.
 
b) It could not readily have been produced by the subject’s clinical state, environmental or toxic factors, or other therapies administered to the subject.
 
c) Disappears or is decreased upon removal of the device.
 
d) It follows a known response pattern to treatment with the device.
 

Unlikely	
In general, this category can be considered applicable to those AEs which, after careful medical consideration at the time they are evaluated, are judged likely to be unrelated to the device. An AE may be considered unlikely if or when (must have two):
 
 
a) It does not follow a reasonable temporal sequence from application of the device.
 
b) It could not readily have been produced by the subject’s clinical state, environmental or toxic factors, or other therapies administered to the subject.
 
c) Disappears or is decreased upon removal of the device.
 
d) It does not follow a known or expected response pattern to treatment with the device.
 

Unrelated	
This category applies to those AEs that, after careful consideration, are clearly and incontrovertibly due to extraneous causes (disease, environment, etc.) and determined with certainty to have no relationship to the study device.

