### 5.7.3. Ulcer Infection Assessment

The presence/absence of infection at the study ulcer site will be documented at each visit.

**IMPORTANT:** If the study ulcer is considered infected during the screening phase, or at Randomization visit (TV1), the subject is considered a screen fail and is excluded from participation in the trial at that time. The infection must be treated, and symptoms resolved before the subject may be re-screened (one time only, according to Section 6.1.2). Additionally, and per exclusion criterion 2, the subject must not be taking antibiotics for a DFU infection.

If the study ulcer becomes infected after the subject is randomized, it must be recorded as an AE. The study ulcer infection may be treated, per investigator judgement, and the subject may remain in the study unless a prohibited medication or treatment is used (see Section 5.14.1).

*PriMatrix is contraindicated for infected ulcers.* In the event of a study ulcer infection in the PriMatrix treatment group, PriMatrix may be re-applied after the study ulcer infection has been treated and no longer demonstrates signs/symptoms of the infection.

All infections will be followed until resolved or the subject is withdrawn or discontinued. If an infection progresses to tissue necrosis requiring deep debridement which exposes bone, tendon or capsule, the subject must be withdrawn.

In no case, does the presentation of infection alter the study schedule of events nor allow the subject additional days of treatment.

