## 5.15. Adverse Events

### 5.15.1. Definitions

An adverse event (AE) is defined as any untoward medical occurrence occurring in a clinical trial. An AE does not necessarily have a causal relationship with the device. A device-related AE can be any unfavorable and unintended sign, symptom, or disease temporally associated with the use of a study device, whether or not related to the device.

**For the purposes of this study, only AEs that are possibly, probably, or definitely related to the study ulcer, study treatment, and/or study procedures are to be recorded.** All events starting or worsening beginning at SV2 through Treatment Visit Week 13 and unscheduled visits will be collected. Follow-up treatment and evaluation should continue until the AE has resolved or until 2 weeks after the final visit, whichever occurs first.

AEs not related or unlikely related to the study treatment, study ulcer and/or study procedures are not to be recorded for this study.

A Serious Adverse Event (SAE) is defined as any AE that:

- Results in death

- Is life threatening (the subject is at immediate risk of dying from the adverse experience)
- Requires subject hospitalization or prolongs existing hospitalization
- Results in persistent or significant disability/incapacity
- Is a congenital anomaly/birth defect
- Important medical events that may not result in death, be life-threatening, or require hospitalization may be considered a serious adverse device effect when, based upon appropriate medical judgment, they may jeopardize the subject or subject and may require medical or surgical intervention to prevent one of the outcomes listed in this definition.

For the purposes of this study, only SAEs that are possibly, probably, or definitely related to the study ulcer, study treatment, and/or study procedures are to be recorded. All events starting or worsening after the first randomized treatment through Treatment Visit Week 12 will be collected. Follow-up treatment and evaluation should continue until the SAE has resolved or until 2 weeks after the final visit, whichever occurs first.

SAEs not related or unlikely related to the study treatment, study ulcer and/or study procedures are not to be recorded for this study.

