12.7. Adverse Events

Adverse Events will be coded using the MedDRA Medical Dictionary. AE's are defined as events with an onset after screening visit 1. Treatment Emergent AE's (TEAE) are defined as events with an onset on or after the randomized treatment. TEAEs will be summarized by treatment group, System Organ Class, and preferred term. The following TEAE summaries will be provided:

- TEAEs by severity grade
- TEAEs by relationship to study treatment.

In addition, separate summaries of Serious Adverse Events, and Adverse Events resulting in discontinuation of study treatment will be presented.

The safety population will be used for the safety analyses. Subjects will be counted only once for subject-based analysis. If the same event changes in severity for a subject, the worst severity will be reported.

An Adverse Event is considered treatment emergent if (1) it was not present at Screening Visit 1, and it is not a chronic condition that is part of the subject's medical history; or (2) it is present at Screening Visit 1 or as part of the subject's medical history, but the severity or frequency increases during treatment.

Treatment-emergent adverse events (TEAE) will be summarized for each treatment group by body system and preferred term. The severity of all adverse events will be determined by the investigator's judgment and classified as mild, moderate or severe.

Treatment groups will be compared with respect to the incidence of Adverse Events (all and TEAEs) and the proportion of subjects withdrawing from the study for Adverse Events by reason of withdrawal. Comparisons will be made overall, by body system and by preferred term and will be further categorized by severity and by study device relationship.

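### Two criteria in the Unlikely row of the causality table favour relatedness, so related adverse events can go unrecorded, and the table gives no usable set of criteria for control-arm events

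*Protocol*

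**What the plan says.** **What is recorded.** Protocol 5.15.1 states that "only AEs that are possibly, probably, or definitely related to the study ulcer, study treatment, and/or study procedures are to be recorded". It adds that "AEs not related or unlikely related to the study treatment, study ulcer and/or study procedures are not to be recorded for this study", and for serious events that "SAEs not related or unlikely related to the study treatment, study ulcer and/or study procedures are not to be recorded for this study".

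**How the rating is made.** Protocol 5.15.3 calls Table 2 guidelines and treats an AE as device-related when there is a reasonable possibility that the device caused or contributed to it. The Possibly row reads "An AE may be considered possible if or when (must have two" and the Unlikely row "An AE may be considered unlikely if or when (must have two", each followed by four criteria. Probable requires three of the same four, and Definitely requires all of a list of three. The criterion "Disappears or is decreased upon removal of the device" appears in identical words under Probable, Possibly and Unlikely. No rule says which category applies when an event meets more than one.

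**Other recording rules.** Protocol 5.7.3 says: "If the study ulcer becomes infected after the subject is randomized, it must be recorded as an AE". On serious events the documents disagree. Protocol 5.15.1 and the special SAE instructions in 5.15.5 restrict recording or reporting to related SAEs. The list of recordable events in 5.15.5, Protocol 8.12.4, and SAP 3.4 and 12.6 refer to all SAEs.

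**Use of the data.** SAP 12.7 states: "Treatment groups will be compared with respect to the incidence of Adverse Events (all and TEAEs". The trial is open-label (Protocol 3 and 8.5).

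**The concern.** In most trials a poor causality scale mislabels events. Here the rating also decides whether a non-serious event enters the database, because an AE rated Unlikely is not recorded. Two of the four criteria under Unlikely point towards relatedness, and any two criteria are enough. An investigator who follows the checklist can therefore reach Unlikely on evidence that supports relatedness.

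The second problem is the reference to the device. Protocol 5.15.1 makes an event recordable if it is related to the ulcer, the treatment or the procedures. The criteria for timing, removal and response pattern speak only of the device, and control subjects receive standard of care without PriMatrix (Protocol 3.1). If the same ulcer event is easier to rate as related in one arm, part of any between-arm difference in AE incidence would reflect recording and not safety.

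**Working it through.** The plan gives no figure on this point, so the check is of the table's logic.

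**Inputs (Protocol 5.15.3, Table 2).** Write each criterion in the form that supports relatedness:

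- a: the timing fits application of the device
- b: the subject's condition or other factors do not readily explain the event
- c: the event resolves or lessens when the device is removed
- d: the event fits a known response to the device

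Rules as written:

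- Definitely: a, b and d all true (this row words b slightly differently; I treat it as the same criterion)
- Probable: at least 3 of a, b, c, d
- Possibly: at least 2 of a, b, c, d
- Unlikely: at least 2 of not-a, b, c, not-d

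**Count.** Let n be the number true among b and c, and m the number true among a and d. Possibly needs n + m ≥ 2. Unlikely needs n + (2 − m) ≥ 2, that is n ≥ m.

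| n | m | Patterns | Highest related category | Also Unlikely? |
|---|---|---|---|---|
| 0 | 0 | 1 | none | yes |
| 0 | 1 | 2 | none | no |
| 0 | 2 | 1 | Possibly | no |
| 1 | 0 | 2 | none | yes |
| 1 | 1 | 4 | Possibly | yes |
| 1 | 2 | 2 | Probable (one is Definitely) | no |
| 2 | 0 | 1 | Possibly | yes |
| 2 | 1 | 2 | Probable | yes |
| 2 | 2 | 1 | Definitely | yes |

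- Possibly or higher: 1 + 4 + 2 + 1 + 2 + 1 = 11 of 16.
- Of these, also Unlikely: 4 + 1 + 2 + 1 = 8.
- Probable patterns (at least three true): 2 + 2 + 1 = 5, of which 2 + 1 = 3 are also Unlikely.
- Definitely patterns: 2 (a, b, d with or without c), of which 1 is also Unlikely. With all four true, an event meets Definitely, Probable, Possibly and Unlikely together.
- The two patterns with only a or only d true meet no listed rule.

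**If b and c are negated under Unlikely.** Unlikely then needs at least two of the four to be false, so n + m ≤ 2. No Probable or Definitely pattern qualifies. Patterns with exactly two true still meet both Possibly and Unlikely: 4!/(2!·2!) = 6. Five of these overlap already (4 + 1 in the table), and the sixth, a and d only, is new. If the more related category then prevails, 11 patterns fall in Possibly or higher and 16 − 11 = 5 in Unlikely, with none unassigned.

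**Control arm, literal reading.** Assume that the device means PriMatrix; Protocol 12.3 lists the device separately from standard-of-care supplies. Then a, c and d cannot be true. At most one criterion (b) is met, short of the two needed for Possibly, while not-a and not-d always satisfy Unlikely. Negating b and c does not change this.

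**The case against.** The best defence is that Table 2 is guidance and not an algorithm. Protocol 5.15.3 sets a reasonable-possibility rule, each row opens with an overall medical judgement, and the criteria say what an event may be considered. An event with all four features pointing to the device does not fit the opening text of the Unlikely row. This stands as a reason to expect that many investigators would rate sensibly. It does not rescue the row: each list carries a required number of criteria, two of the Unlikely criteria point the wrong way, and the reasonable-possibility rule concerns the device only.

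Three stronger inferences are tempting, and the documents do not support them.

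- **That the table controls all AE recording.** Study-ulcer infections after randomization must be recorded in both arms without a causality test (Protocol 5.7.3). Several passages call for all SAEs, although others conflict. Even if all SAEs are recorded, the rating still matters for them, because expectedness is determined only for serious events rated at least possibly related (Protocol 5.15.4).
- **That control-arm events cannot qualify.** Protocol 5.15.1 and the opening text of the Definitely row admit relatedness to the ulcer or the procedures, and neither needs PriMatrix. The supportable statement is that the listed criteria give no usable way to apply that rule in control subjects.
- **That 8 of 11 measures how many events are lost.** It counts logical patterns. Five of the eight have exactly two criteria true and would remain ambiguous after the wording is corrected. The overlap that comes only from the two un-negated criteria is the three patterns that reach Probable or higher.

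**Conclusion.** The Unlikely row is wrong as written. Because an Unlikely rating means that an AE is not recorded, a related event can be left out of the safety data by following the table. The clear exposure is non-serious AEs other than study-ulcer infections. The pattern counts assume that the criteria are applied literally and that the four features can each be true or false independently.

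The device-only wording is a separate weakness. It creates a risk of arm-dependent recording in an open-label trial whose SAP compares AE incidence between arms. A reader might infer that the comparison is biased by construction or that the safety objective is defeated. The documents do not establish either: the size of any under-recording or imbalance depends on how investigators used the table, and it cannot be computed from the plan. The primary and secondary efficacy results are not affected.

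**What to change.** 1. In the Unlikely row, negate the criterion on other explanations and the one on device removal.
2. State that when an event meets two categories, the more related one applies. The wording change alone leaves six patterns in both Possibly and Unlikely.
3. Reword the criteria in all rows to cover the assigned study treatment, the study ulcer and study procedures, so that they work in both arms.
4. Reconcile the passages on SAE recording: Protocol 5.15.1 and the special SAE instructions in 5.15.5 against the event list in 5.15.5, Protocol 8.12.4, and SAP 3.4 and 12.6.

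Prospectively the cost is a table correction and a site memo. SAP 10.4 reports that screening and enrolment were ended early, so most of the work is retrospective. Events already classed Unlikely should have no AE entry to re-rate; they would have to be sought in source documents, in both arms and by the same procedure. The reported AE count may rise. If the search is not feasible, the study report should state the limitation beside the between-arm AE comparison.

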#### 5.15.4. Adverse Event Expectedness

If an AE is determined to be serious and related, either possibly, probably, or definitely related, to the study device or procedure, a determination of expectedness will be made. Expectedness is specifically related to the functioning of the product or the conduct of the procedure and is NOT related to whether the study team perceived that the AE might have happened in the subject. That is, the question is “Have we seen this SAE in relation to the product/procedure?” and is **not** “Did we think this SAE would happen in this subject?”.

A SAE is expected, that is “**Anticipated**” if the SAE is (1) related to the product or procedure **and** (2) the nature, severity, or frequency of the SAE has been seen previously either in personal experience or documented in literature. Note: The vast majority of related SAEs are Anticipated.

Conversely, a SAE is not expected, that is “**Unanticipated**” if the SAE is (1) related to the product or procedure **and** (2) the nature, severity, or frequency of the SAE has **NOT** been seen previously either in personal experience or documented in literature. Note: The vast minority of related SAEs are unanticipated.

Therefore, an unanticipated adverse device effect (UADE) is defined as any serious adverse effect on health or safety or any life-threatening problem or death caused by, or associated with, a device, if that effect, problem, or death was not previously identified in nature, severity, or degree of incidence in the investigational plan or IFU, or any other unanticipated serious problem associated with a device that relates to the rights, safety, or welfare of subjects.

[figure not shown]
The decision tree in figure 3 should be used when determining expectedness.

For the purposes of this study, the following AEs commonly occur in individuals with DM and DFUs and are thereby defined as Anticipated if they were to occur:

- Ulcer enlargement, tunneling and/or undermining
- Malodor
- Erythema
- Edema
- Maceration
- Excessive drainage
- Development of a new ulcer,
- Ulcer infection or abscess,
- Osteomyelitis
- Trauma/falls and
- Amputation

Questions about any AEs or SAEs should be directed to the sponsor for clarification; however, the ultimate decision for grading severity and expectedness resides with the study investigators.

Figure 3: SAE Expectedness Determination Decision Tree

#### 5.15.5. Adverse Event Reporting Procedures

All AEs related to study treatment, study ulcer and/or study procedures spontaneously reported by the subject and/or in response to an open question from study personnel or revealed by observation, physical examination or other diagnostic procedures will be evaluated.

At each visit, after the subject has had the opportunity to spontaneously mention any problems, the investigator should inquire about AEs by asking standard questions such as:

- “Have you had any (other) medical problems since your last visit / assessment?”
- “Have you taken any new medicines since your last visit /assessment?”

The following AEs will be recorded on the appropriate eCRF:

- All AEs related to study treatment, study ulcer and/or study procedures occurring after the 1st randomization treatment.

- All SAEs occurring after signing of ICF through the last study visit

When possible, signs and symptoms indicating a common underlying pathology should be noted as one comprehensive event.

**Special instructions for SAEs**

Study centers are instructed to report SAEs to Integra within 5 business days of becoming aware of the SAE.

SAEs must be reported by the investigator to Integra by completing the eCRF SAE Form. Only SAEs that are considered causally related to the study device or procedures need to be reported. Reporting will utilize the standard AE eCRF. Note: Follow-up information on the SAE may be requested by the sponsor.

5.15.6. Adverse Event Follow-up

All AEs will be followed until resolution or stabilization to the best of the site’s ability. Any subjects reporting SAEs that have not resolved by their last treatment visit will be followed via phone or clinic visit through resolution or 14 days post final visit, whichever comes first.

5.16. Method for Assigning Eligible Subjects to Treatment (i.e., Randomization)

Once it has been determined that a subject meets all eligibility criteria, subjects will be assigned to one of the following treatment groups, based on a randomization schedule provided by the sponsor.

Randomization is accomplished through the Clindex EDC system. After entering your name and password, you will go into the RDE System and click on Subject List or Visit Manager. After selecting the subject to be randomized, click on the Randomization eCRF in the Randomization Visit. You will be asked to answer the following:

- Did the subject meet all eligibility criteria?
  - Select Yes if eligible
  - Select No if not eligible
- Is the percent ulcer reduction  $\leq 30\%^*$  since the initial screening visit?
  - Select Yes if the ulcer decreased in size less than or equal to 30% **or** if the ulcer got bigger
  - Select No if the area of the ulcer decreased in size more than 30% during the screening period
  - Enter the size of the decrease or increase
- Is the area of the study ulcer between 1cm^2 and 12cm^2\*?
  - Select Yes if between 1 and 12cm^2

- Select No if not between 1 and 12cm^2
- Enter the size of the ulcer area.

***\*Important: Rounding up or down is not allowed to achieve eligibility. For instance, if the ulcer decreased 30.1% between SV1 and Randomization, the subject is still ineligible for randomization. Similarly, if the area of the wound is 0.99cm^2 at either SV1 or Randomization, the subject is ineligible.***

After all of the questions have been answered, you will click on the Save button. Click “Yes” on each of the following pop-up screens. A third screen will pop up with the randomization group: Active or Control. The active treatment is the PriMatrix product (see Section 5.17 below). The control treatment is SOC that has been used during the past two screening visits.

